The nutrient data collected on a sample of the participants will be reviewed to monitor for potential nutritional deficits. In addition, the interventionists will educate participants on how to prevent nutritional deficiencies and will informally monitor nutrient intake. For safety purposes, all participants assigned to the Wt or combined Wt/Na intervention will monitor their heart rate before and after undertaking their program of continuous physical activity. The goal of this assessment will be to achieve a heart rate based on 40-55% of heart rate reserve. Additionally, participants will also be instructed that any physical activity which makes them feel out of breath may be at a higher level of exertion than recommended. This modest level of physical activity should not place most participants at risk. However, participants assigned to the weight reduction arms and also identified as at higher risk for developing cardiac disease as defined by greater than age 50 and the presence of two or more cardiovascular risk factors (male gender, total serum cholesterol >240 mg/dl, history of cigarette smoking, history of diabetes mellitus, or family history of coronary or other atherosclerotic disease prior to age 55) will be further monitored. This information will be recorded prior to the start-up of intervention on the data form for the assessment of risk level in the TOHP physical activity program. It will be the responsibility of interventionists to note in their files for people in the weight/physical activity intervention arms only whether a participant is at higher risk with regard to the possibility of having cardiac disease. Interventionists will also ask these individuals if they are participating in regular physical activity with heart rate in the range of 40-55% of heart rate reserve. If above 55%, that is above program guidelines,

they will be referred to their personal physician for evaluation.

Alternatively, instead of referring a participant to their personal physician, the clinical center could elect to do its own ECG stress test to determine clearance prior to allowing the participant to resume the physical activity component of the intervention.

QUALITY CONTROL

At the clinical centers, quality control will encompass the following areas:

- training and certification of personnel responsible for measuring blood pressure, height and weight;
- training and certification of staff responsible for conducting each of the intervention protocols;
- training and certification of diet interviewers;
- calibration and maintenance of BP devices, including random zero and standard mercury devices;
- calibration and maintenance of other equipment, including scales, height boards;
- inspection and certification of the physical environment of the clinic, with particular attention to the separation of all data collection activities from those related to the delivery of the interventions;
- validation of data collection and coding procedures including monitoring adequacy of the 24-hour urine specimens; and
- review of laboratory specimen handling, shipping, and storing.

The Coordinating Center will be responsible for the verification and validation of all data entry, the computer editing of forms, and the generation of reports monitoring the quality of the data being collected. These monitoring reports will include reports on the screening and

randomization process, on the performance of the central laboratory and nutrition center, on the accuracy of form completion and of BP readings, and on the completeness of the data base.

To implement quality control monitoring, the clinic coordinator will be responsible for certification and recertification procedures, and local data collection, including the "blindness" of data collectors to group assignments. She or he will report problems to the local clinical center Principal Investigator and the Coordinating Center on a regular basis. A Quality Assurance Subcommittee, including representatives from the clinical centers, the NHLBI Program Office, the Coordinating Center, the central laboratory and the nutrition center will periodically review reports, provided by the Coordinating Center, tabulating errors and citing deviations from protocol and will help clinical centers which have been recognized as having a problem or who have requested help in any of these areas.

DATA ANALYSES

To assess the effects of weight loss, sodium restriction, and their combination, the mean changes in DBP at 36 months in the various groups will be compared. Additionally, the average of all BPs obtained during the trial in the various groups will be compared. The analysis of variance for a two-by-two factorial design will be used to test the main effects of weight loss and of sodium restriction. Multiple regression analyses will be performed to adjust for other covariates, such as age, sex, and initial weight and urinary sodium. To reduce the impact of regression to the mean and to improve the error variance, as well as to adjust for any imbalance, mean initial DBP will also be included in the model. To compare DBP changes in two of the four groups, such as the combined intervention versus placebo, comparisons of means

with a t-test and multiple regression analyses will similarly be used. These methods can also be used to explore the effect of the combined intervention compared to a single intervention such as weight loss alone. More sophisticated methods of longitudinal data analysis such as computing slopes over time or the use of autoregressive models will be used to explore more complex changes in DBP over time in the various treatment groups (48-50).

Because the effect of treatment may not be uniform across all members of a group, we will also examine the distribution of blood pressure changes. Should these appear not to be normally distributed, we will perform nonparametric tests of significance. To examine the effect of actual compliance to the treatment regimen, we will consider change in DBP as a function of actual change in weight and urinary sodium. This is of particular importance because some members of the control group may seek to implement the intervention strategies on their own.

Censoring of this continuous variable due to incidence of hypertension is a potential problem in this analysis. Once antihypertensive medications are prescribed, blood pressure readings become biased in those subjects who should have the highest levels. For this reason we will attempt to acquire and use termination blood pressures obtained prior to initiation of antihypertensive therapy. Furthermore, individuals who are told they are hypertensive may begin some nonmedical intervention; such as weight loss, on their own, perhaps under the advise of their physicians, even if they do not take medications.

Several strategies may be used to deal with the effects of such biases. The primary analysis will use the termination blood pressure as defined in Phase I of TOHP. This is the last recorded blood pressure prior to the initiation of

drug therapy. This includes blood pressures measured after becoming an endpoint according to the definition of SBP $_{\geq}140$ mmHg or DBP $_{\geq}90$ mmHg, but prior to starting medication. Because it is recognized that these latter measurements may be biased, secondary analyses will be performed to confirm the results of the primary analysis. These include an analysis of blood pressures taken at the time of diagnosis for those who become hypertensive, imputing minimum values of 90 mmHg for DBP and 140 mmHg for SBP for those who go on BP medications, and also a multivariate repeated measures analysis. The latter approach would use all measured blood pressures on an individual either including or excluding those following diagnosis. In this way, both the within-person variation as well as an effect of "self-intervention" could be taken into account.

Secondary endpoints in the trial, including changes in SBP and the development of diastolic and systolic hypertension, will also be examined. The former will be evaluated in the same manner as changes in DBP described above. For the hypertension endpoints, crude relative risks and a chi-square test will be calculated for each hypothesis to compare cumulative incidence rates over the duration of the study. We will compute Kaplan-Meier incidence-free survival curves and the logrank test statistic. A Cox proportional hazards regression analysis will be performed to adjust for potential confounders such as baseline BP, age, sex, and race.

Intermediate variables such as urinary sodium and body weight will be monitored on a regular basis and compared across intervention groups.

This trial will also provide the opportunity to explore any differential response to intervention by race, and gender, as well as body mass index,

waist to hip ratio, cigarette smoking habits, pulse rate, family history of hypertension, and baseline electrolyte excretion. Currently we expect to recruit a sample with approximately 21% blacks and 33% women. While power will not be adequate to test the effect of the interventions within these subgroups, we will explore any differences among them.

STUDY ADMINISTRATION

The administrative structure of TOHP consists of committees and subcommittees with representatives from the participating units.

1. Steering Committee

The Steering Committee will be the central governing body of TOHP. It will be made up of the principal investigators from each of the clinical centers as well as one representative each from the Coordinating Center and the NHLBI. Each participating unit will have one vote, normally cast by the Principal Investigator. In addition, officers of the study (Chairman and Vice Chairman) will each have one vote regardless of whether or not they are attached to a clinical center. During Phase II, the Steering Committee will meet face-to-face at least semi-annually to review the progress of the trial. Each center will be required to be represented at each meeting by at least the Principal Investigator (or designated co-investigator) and one other representative from that clinic. The Study Chairman will serve as chairman of the Steering Committee.

The six subcommittees of the Steering Committee that were active in the first phase of TOHP will continue. Their activities are summarized below:

The Design and Analysis Subcommittee will be responsible for reviewing overall design features, e.g., sample sizes, blinding, and stratification;

for proposing specific data analyses; for reviewing requests from investigators for data analyses and recommending priorities for analysis.

The Eligibility and Recruitment Subcommittee will recommend the inclusion and exclusion criteria for participant eligibility and is responsible for development of strategies and resources to aid the clinical centers in effective and efficient recruitment. It will also be responsible for reviewing recruitment reports from the Coordinating Center in order to identify problems and propose solutions on a clinic-by-clinic basis.

The Interventions Subcommittee will develop intervention methods and materials, monitor compliance outcomes, and, if necessary, propose modifications to the intervention protocols for review and approval by the Steering Committee.

The Data Collection and Quality Assurance Subcommittee will recommend to the Steering Committee the data set to be collected from TOHP participants, review data forms, and be responsible for collaborating with the CC in the development and implementation of quality assurance programs.

The Clinic Coordinators Subcommittee will be composed of one representative from each clinical center, who will be responsible for assisting the Principal Investigator in organizing the center staff, facilities, and tasks, and representatives from the Coordinating Center.

The Publications and Presentations Subcommittee will be responsible for establishing and implementing procedures for review of publications and presentations of TOHP materials.

In Phase 2, an Endpoints Subcommittee will conduct a blind review of the study forms and, as necessary, the medical records of participants who are considered to have had hypertensive endpoints. By simple majority vote, the subcommittee will confirm or disconfirm each potential hypertensive endpoint.

2. Executive Committee

The TOHP Executive Committee will be composed of the study chairman and study vice-chairman, selected by the Steering Committee, the NHLBI Project Officer, and the Director of the CC. This group will discuss and help formulate and implement all Steering Committee decisions related to the maintenance and conduct of TOHP within the guidelines established by the protocol.

3. Data and Safety Monitoring Committee

The Data and Safety Monitoring Committee (DSMC) will be responsible for reviewing the initial study protocol, for assessing accumulating study data for adverse and/or beneficial intervention effects, and ensuring that risks to subjects are minimized. DSMC members will be appointed by the NHLBI Project Office based on consultation with the Executive Committee.

I. LITERATURE CITED

- 1. Subcommittee on Definition and Prevalence of the 1984 Joint National Committee. Hypertension prevalence and the status of awareness, treatment, and control in the United States. Hypertension 1985;7:457-468.
- 2. Hypertension Detection and Follow-up Program Cooperative Group. Five-year findings of the Hypertension Detection and Follow-up Program. I. Reduction of mortality of persons with high blood pressure, including mild hypertension. JAMA 1979; 242:2562-71.
- 3. Hypertension Detection and Follow-up Program Cooperative Group. Five-year findings of the Hypertension Detection and Follow-up Program. II.

 Mortality by sex, race and age. JAMA 1979;242:2572-77.

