The variance of the change from baseline (x_1) to the unweighted average of the time-specific means at 6 months through 36 months (x_3) can be written as:

can be written as:
$$\sigma_{2}^{2} = V(x_{3} - x_{1}) = (\sum (\sigma_{p}^{2} + \sigma_{a}^{2}/n_{i} + \sigma_{e}^{2}/k_{i}n_{i}) + 2\sum \rho_{i,j}\sigma_{p}^{2})/36$$

$$i$$

+
$$(\sigma_{p}^{2} + \sigma_{a}^{2}/n_{o} + \sigma_{e}^{2}/k_{o}n_{o}) - \sigma_{p}^{2} \Sigma \rho_{o,i}/3$$

where i and j represent the 6 measurement times from 6 months through 36 months

 n_i = the number of visits at time i

 $\ensuremath{k_{\scriptscriptstyle i}}$ = the number of measurements per visit at time i (=3) and all summations are over times 6 to 36 months.

The following parameter estimates are applied:

a) The variance components were based on race and gender specific estimates from a population of 991 individuals aged 30-69 years (41). These were combined by taking weighted averages using the age, sex and race distribution of the Phase I participants. This population was 30% female, 15% black, with 80% aged 30-49 and 20% aged 50-54. The average variance components are:

$$\sigma_{p}^{2} = 100.4$$

$$\sigma_{a}^{2} = 27.3$$

$$\sigma_{e}^{2} = 7.6$$

b) Tracking correlations of 0.58 (42) for DBPs taken four years apart and 0.85 (43) for those taken one year apart have been published. For any time interval the relationship of the true correlation (ρ_t) to these observed correlations (ρ_o) is a function

of the number of visits (n) and measurements per visit (k) as follows:

$$\rho_{t} = \rho_{o} \times (\sigma_{p}^{2} + \sigma_{A}^{2}/n + \sigma_{e}^{2}/nk)/\sigma_{p}^{2}$$

with the various components as defined previously. These data suggest true 4-year and 1-year correlations of 0.85 and 0.91.

Interpolating from these results, we estimate that the true tracking correlations over 6, 12, 18, 24, 30 and 36 months are 0.95, 0.91, 0.90, 0.89, 0.88, and 0.87, respectively.

Using the above parameters, the estimated variance of DBP change from baseline to termination is 6.78^2 within each treatment group. The estimated variance of DBP change from baseline to the average of all follow-up visits is 5.24^2 .

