Using the assumptions for change from baseline to termination a sample size of 621 per group or a total of 2484 is needed to achieve 80% power for all three hypotheses. With the proposed sample size of 2250 we thus do not achieve 80% power to detect a difference of 1.5 mmHg between the combined intervention and the placebo with this endpoint. We do, however, have more than adequate power to address the main hypotheses of weight loss and sodium restriction. The power for each hypothesis for various differences in DBP change from baseline to termination is shown in Table 1. As indicated, with 80% power, we can detect an effect of 1.2 mmHg for overall weight loss or sodium restriction or a difference of 1.6 mmHg between the combined intervention and placebo groups. The last column of Table 1 reflects

12/15/1992

Table 1 Power (%) for a primary hypothesis with a total sample size of 2250 using DBP change from baseline to termination.

Difference in DBP change	Overall effect of weight loss or sodium restriction	Combined vs. control *
1.0	69.5	36.6
1.1	78.8	44.6
1.2	86.2	52.7
1.3	91.6	60.8
1.4	95.3	68.4
1.5	97.5	75.3
1.6	98.8	81.3
1.7	99.4	86.3
1.8	99.8	90.3
1.9	99.9	93.4
2.0	100.0	95.6

^{*} The power for the combined versus weight loss and for the combined versus Na restriction is the same as that for combined versus control.

the power to test differences between any two groups, including the combined vs. sodium restriction groups and the combined vs. weight loss groups. We thus have 80% power to detect a difference of 1.6 mmHg in the latter two comparisons, which may not be adequate.

The power using DBP change from baseline to the average of all follow-up blood pressures is given in Table 2. The power is greatly increased by using the additional data. We have over 90% power to detect an effect of 1.0 mmHg for overall weight loss or sodium restriction, and almost 80% power to detect a difference of 1.2 mmHg between the combined intervention and placebo group, or either single intervention group.

- B. A secondary endpoint to be considered is the change in systolic blood pressure (SBP) over the course of the trial. Similarly to DBP, the outcomes will be defined as the change from baseline to termination SBP at 36 months or before starting BP medication, and the change from baseline to the average of all SBP's from 6 months to 36 months. The assumptions used for SBP are identical to those for DBP outlined above, with the following parameter estimates:

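### The printed 4-year DBP correlation (0.58), variance components and correction formula cannot give the stated true correlation of 0.85, on which the DBP standard deviations, N = 621 and Tables 1 and 2 rest

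*Protocol*

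**What the plan says.** All of this stands in the Protocol, Sample Size and Power, part A.

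- Item 1(a) gives the DBP variance components: between-person 100.4, between-visit 27.3, within-visit 7.6.
- Item 1(b) gives the observed correlations: "Tracking correlations of 0.58 (42) for DBPs taken four years apart and 0.85 (43) for those taken one year apart have been published". It converts observed to true correlation by a formula in the number of visits n and readings per visit k, "with the various components as defined previously", and reports: "These data suggest true 4-year and 1-year correlations of 0.85 and 0.91". It does not give n and k for either cited source.
- It then interpolates: "true tracking correlations over 6, 12, 18, 24, 30 and 36 months are 0.95, 0.91, 0.90, 0.89, 0.88, and 0.87".
- From these it derives an SD of DBP change of 6.78 (baseline to termination) and 5.24 (baseline to the average of follow-up).
- The text before Table 1 concludes that "a sample size of 621 per group or a total of 2484 is needed to achieve 80% power for all three hypotheses". It adds that 2250 participants give 80% power for 1.2 mmHg on a main effect and 1.6 mmHg between two groups.
- On Table 2 it says: "We have over 90% power to detect an effect of 1.0 mmHg for overall weight loss or sodium restriction".

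**The concern.** The correction multiplies the observed correlation by total variance over between-person variance. That multiplier is largest for a single visit with a single reading and shrinks as either number grows, so it has a ceiling that can be checked without seeing the cited source. The stated 0.85 lies above the ceiling.

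The figure carries weight. The 36-month correlation is interpolated from it, and that correlation sets the variance of the primary endpoint, the required sample size and the power tables. A lower correlation means a larger variance of change and less power on the stated method.

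**Working it through.** **Inputs** (Protocol, Sample Size and Power, part A): σp² = 100.4, σA² = 27.3, σe² = 7.6; observed 4-year correlation 0.58; z values 2.394 and 0.84; censoring 31.1%; 2250 in total, so 1125 per side for a main effect and 562.5 per group for a pairwise comparison.

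**1. The protocol's figures, taking 0.85 as given.**
- Straight line from 0.91 (year 1) to 0.85 (year 4): ρ at 36 months = 0.91 − 0.06 × 2/3 = 0.87, as stated.
- σ₁² = 2 × 100.4 × (1 − 0.87) + 2 × (27.3 + 7.6/3)/3 = 26.10 + 19.89 = 45.99, SD 6.78, as stated.
- N = 2 × 45.99 × (2.394 + 0.84)² / (1.5² × 0.689) = 620.6, stated as 621.
- Power = Φ(Δ / √(2σ²/(N × 0.689)) − 2.394) returns the Table 1 entries checked to within 0.1 point, for example 75.3% for combined versus control at 1.5 mmHg.
- The Table 2 entries checked reproduce from SD 5.24. That SD recomputes as 5.19, about 1% lower, which is not material.

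Everything after 0.85 therefore hangs together.

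**2. The conversion itself.** True ρ = observed ρ × (100.4 + 27.3/n + 7.6/(nk)) / 100.4.

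| n | k | multiplier | 0.58 becomes |
|---|---|---|---|
| 1 | 1 | 1.348 | 0.782 |
| 1 | 2 | 1.310 | 0.760 |
| 1 | 3 | 1.297 | 0.752 |
| 2 | 1 | 1.174 | 0.681 |
| 3 | 3 | 1.099 | 0.637 |

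Reaching 0.85 needs a multiplier of 0.85/0.58 = 1.466, that is, error variance of 0.466 × 100.4 = 46.7. The components supply at most 27.3 + 7.6 = 34.9. Alternatively, the observed correlation would have to be at least 0.85/1.348 = 0.631.

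**3. The other conversions.** With n = 4 and k = 3, values chosen here because they fit, the 1-year figures come out: DBP 0.85 gives 0.913 (stated 0.91) and SBP 0.81 gives 0.853 (stated 0.85). For 4-year SBP, 0.67 gives 0.838, 0.818 and 0.811 at one visit with 1, 2 and 3 readings. These bracket the stated 0.83 without hitting it; rounding of 0.67 could explain that. Only the 4-year DBP value lies outside the attainable range.

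**4. Consequence if 0.58 and the components stand.** Same straight-line interpolation, raw-change SD and 31.1% censoring. The columns use a 4-year ρ of 0.782 (the ceiling) and 0.752 (one visit, three readings).

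| | Stated | 0.782 | 0.752 |
|---|---|---|---|
| ρ at 36 months | 0.87 | 0.824 | 0.805 |
| SD, termination | 6.78 | 7.43 | 7.69 |
| N per group for 1.5 mmHg | 621 | 745 | 798 |
| Combined vs control, 1.5 mmHg | 75.3% | 66% | 63% |
| Combined vs control, 1.6 mmHg | 81.3% | 73% | 69% |
| Main effect, 1.2 mmHg | 86.2% | 78% | 75% |
| 80% detectable, main effect (mmHg) | 1.2 | 1.22 | 1.26 |
| 80% detectable, two groups (mmHg) | 1.6 | 1.73 | 1.79 |
| SD, average of follow-up | 5.24 | 5.49 | 5.61 |
| Table 2 main effect, 1.0 mmHg | 91.4% | 88% | 87% |
| Table 2 two groups, 1.2 mmHg | 78.6% | 74% | 72% |

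For the first column: σ₁² = 200.8 × (1 − 0.8244) + 19.89 = 55.15.

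**5. Offsets elsewhere in the plan, at 0.782.**
- Data Analyses puts initial DBP in the model. A nine-reading mean has variance 100.4 + 9.94 = 110.34, so the residual variance is 110.34 × (1 − (0.8244 × 100.4/110.34)²) = 48.26, SD 6.95. Combined versus control at 1.5 mmHg is then 73%.
- With 10% missing in place of 31.1% and the raw-change SD, N is about 570 per group and power at 1.5 mmHg is 79%.

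**The case against.** The strongest reply is that the mismatch does not say where the error lies. If 0.58 is a misprint for about 0.63 or more, 0.85 and everything after it stand. The cited source and its n and k are not visible. The reference to components defined earlier could also be read as meaning the symbols rather than the numerical estimates in item 1(a), and a published correlation is properly corrected with the error structure of its own population. This stands in part. It rules out declaring 0.85 the wrong figure. It does not make the printed figures agree: the section gives one set of DBP components, and the natural reading is that they enter the formula.

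A reader might also infer that the trial's power is overstated on balance. The documents do not support that. The protocol itself calls the 31.1% censoring conservative, and its primary analysis keeps pressures measured after a hypertension endpoint but before drug treatment. With 10% missing, power at the ceiling correlation is 79%, above the stated 75.3%. Baseline adjustment alone recovers most of the loss. Both are separate assumptions, however. They would raise the power at 0.85 as well, and they cannot make 0.85 follow from 0.58.

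Finally, no design decision turns on this. The protocol already concedes that 2250 falls short of 80% for combined versus control at 1.5 mmHg, and main effects of 1.5 mmHg keep over 90% power (94% at 0.782, 93% at 0.752).

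**Conclusion.** The point holds as an internal contradiction. For 4-year DBP, the observed correlation, the components and the formula as printed have a ceiling of 0.782, and the protocol states 0.85. Which of the figures is wrong cannot be settled from the document.

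If 0.58 and the components are right, then on the stated method N for the termination endpoint rises by at least 20% (745/621 = 1.20). Combined-versus-control power at 1.5 mmHg falls by about 9 points or more. Three sentences in the power text fail: 80% power at 1.2 mmHg for main effects, 80% at 1.6 mmHg between groups, and over 90% at 1.0 mmHg for the averaged endpoint. The Table 2 losses are smaller, about 3 to 7 points in the entries shown. These sizes assume straight-line interpolation, the raw-change SD and 31.1% censoring, and they describe the stated calculation rather than the net power of the planned analysis.

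**What to change.** In Sample Size and Power, part A, item 1(b), reconcile 0.58, the variance components and 0.85 against the cited 4-year source, and state the n and k used for each conversion.

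- If 0.58 is a misprint or other components were used, correct or state them. The SDs, N and tables then stand.
- If 0.58 and the components are right, replace 0.85 by the value the formula gives at the source's n and k (at most 0.78). Re-interpolate 18 to 36 months, and restate both SDs, N, Tables 1 and 2 and the detectable differences. Add a sentence saying that baseline adjustment and less censoring than 31.1% may offset the loss, with the power under each.

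Keep 2250. The cost is wording, possibly two tables, and perhaps a less favourable stated power; no additional participants are needed.
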